**Table 21: Overall visit response algorithm**

Target lesions	Non-target lesions	New lesions	Overall response
CR	CR	No or NE	CR
CR	NA	No or NE	CR
CR	Non CR/Non PD	No or NE	PR
CR	NE	No or NE	PR
PR	Non PD or NE or NA	No or NE	PR
SD	Non PD or NE or NA	No or NE	SD
NE	Non PD or NE or NA	No or NE	NE
PD	Any	Yes or No	PD
Any	PD	Yes or No	PD
Any	Any	Yes	PD

CR Complete response, PR Partial response, SD Stable disease, PD Progression of disease, NE Not evaluable, NA Not applicable (only relevant if there were no non-target lesions at baseline).

### 8.5.1 Immune-related RECIST 1.1 and confirmation of progression

RECIST 1.1 will be adapted to account for the unique tumor response characteristics seen with treatment of pembrolizumab. Immunotherapeutic agents such as pembrolizumab may produce antitumor effects by potentiating endogenous cancer-specific immune responses. The response patterns seen with such an approach may extend beyond the typical time course of responses seen with cytotoxic agents, and can manifest a clinical response after an initial increase in tumor burden or even the appearance of new lesions. Standard RECIST may not provide an accurate response assessment of immunotherapeutic agents such as pembrolizumab. Therefore, RECIST 1.1 will be used with the following adaptations:

If radiologic (or non-radiological) imaging suggest that the patient has progressive disease (initial PD), tumor assessment should be repeated  $\geq 4$  weeks later in order to confirm PD with the option of continuing treatment per below while awaiting radiologic confirmation of progression.

- If repeat imaging shows  $<20\%$  tumor burden compared to nadir, stable or improved previous new lesion (if identified as cause for initial PD), and stable/improved non-target disease (if identified as cause for initial PD), treatment may be continued/resumed;
- If repeat imaging confirms PD due to any of the scenarios list below, patients will be discontinued from study therapy.

In determining whether or not the tumor burden has increased or decreased, site study team should consider all target lesions as well as non-target lesions.

Scenarios where PD is confirmed at repeat imaging:

- Tumor burden remains  $\geq 20\%$  and at least 5 mm absolute increase compared to nadir;
- Non-target disease resulting in initial PD is worse (qualitative);
- New lesion resulting in initial PD is worse (qualitative);
- Additional new lesion(s) since last evaluation.

In patients who have initial evidence of radiological PD, it is at the discretion of the treating physician whether to continue a patient on study treatment until repeat imaging is obtained. This clinical judgment decision should be based on the patient's overall clinical condition, including performance status, clinical symptoms, and laboratory data. Patients may receive pembrolizumab treatment while waiting for confirmation of PD if they are clinically stable as defined by the following criteria:

- Absence of signs and symptoms indicating disease progression;
- No decline in ECOG PS;
- Absence of rapid progression of disease;
- Absence of progressive tumor at critical anatomical sites (e.g., cord compression) requiring urgent alternative medical intervention.

When feasible, patients should not be discontinued from their study treatment until progression is confirmed. This allowance to continue treatment despite initial radiologic progression takes into account the observation that some patients can have a transient tumor flare in the first few months after the start of immunotherapy, but with subsequent disease response. Patients that are deemed clinically unstable are not required to have repeat imaging for confirmation of progressive disease.

## 8.6 Completion and Closure of the Study

The study will be completed when either:

- The study is terminated at the interim analysis following the DRC review of the ORR and risk/benefit for all patients included in the interim analysis. In this (early termination) situation a Clinical Study Report will be written. The interim analysis will occur once 28 evaluable patients have had the potential to be followed for at

least 24 weeks. In this situation, the last patient, last visit (LPLV) will occur at this point.

*OR*

- The study will complete and the final analysis will occur once all patients (planned 56 evaluable patients) have had the potential to be followed for at least 24 weeks. The last patient, last visit (LPLV) will occur at this point. All data will be reconciled and the database will be locked for analysis. These data will be included in the CSR.

Assuming that there are patients continuing on study treatment at the date of LPLV, the study will be closed once all patients have completed their last dose of study drug or discontinued study drug and have completed their post treatment visit.

- If this closure date occurs after the date of LPLV, only serious safety data will be collected between LPLV and the final closure date. An addendum (or addenda) to the CSR will be generated to report any outstanding serious safety data.
- If this ‘closure date’ occurs before the date of LPLV (because every patient has stopped their study treatment, for example), the study will close at the same time as the date of LPLV.

Study start is defined by the first patient to enter screening, however, the First Patient In (FPI) is when the first patient receives the first dose of study drug.

LPLV is defined as the last visit after all evaluable patients who have had the potential to be followed for at least 24 weeks and includes all data for the final analysis of all evaluable patients.

Study Completion is defined by the date of the LPLV i.e. after the planned number of evaluable patients have had the potential to be followed for at least 24 weeks.

Study Closure is defined by completion of the last dose of study drug and post treatment visit i.e. when the last patient has completed the last dose of study drug or discontinued for any reason and been followed up to the Post Treatment Visit. This date will either be the same as the date of Study Completion or later in time.

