- Optional tumor biopsy (for example at subsequent progression);
- Biomarker sampling.

The Post Treatment Visit will occur 30 days after the patient has discontinued both treatments on study. Patients who withdraw from either or both study treatments prior to disease progression will continue to have tumor imaging assessments every 12 weeks until disease progression is documented (and confirmed, if necessary). The date of disease progression will be captured.

Subsequent to disease progression (confirmed if necessary), patients will continue to have their survival status checked every 12 weeks until death or the Last Patient Last Visit (LPLV) date (see [Section 8.6](#)), whichever is earlier. Survival status can be checked via telephone.

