**Table 9: Study Objectives and Endpoint (assessment)**

Objective	Endpoint (Assessment)
Primary:	

• To assess anti-tumor activity of the combination of BGB324 and pembrolizumab

• Objective response rate (complete response and partial response)

Secondary:	

• To assess the safety of BGB324 and pembrolizumab when given in combination

• The number and frequency of adverse events; assessment of safety laboratory parameters, vital signs and ECGs

• To further assess the anti-tumor activity of the combination of BGB324 and pembrolizumab

• To include Disease Control Rate, Duration of Response; Progression-free Survival; 12-month Overall Survival

• To evaluate the pharmacokinetic profile of BGB324 when given with pembrolizumab.

• Assessment of pharmacokinetic variables including <math>C_{max}</math>, AUC, <math>t_{1/2}</math>

Exploratory:	

• To assess relevant biomarkers

• To assess PD-L1 and Axl expression in patients with TNBC and TN-IBC

• To assess any correlation or association between expression level of PD-L1 and Axl and anti-tumor outcomes such as ORR

• Assessment of relevant biomarkers in tumor and blood which support immune modulation and Axl signaling

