### 8.12.2.3 Progression free survival and overall survival

Kaplan Meier plots of the time to progression and death will be presented, along with the median progression free survival and the estimated survival at 12 months. Descriptive statistics will be used as required, including 95% CI.

PFS is measured from the date of the 1st dose of the 1st cycle until the date of progression (the date on which the progression is initially observed) or the date of death (whichever is earlier). Patients who have not progressed or died before the date of data cut-off (last patient, last visit) will be censored at their last clinical evaluation.

The estimated survival at 12 months will be read from the Kaplan Meier OS curve. The time to death is defined as the time from the date of enrolment until the date of death (from any cause and irrespective of any subsequent ant-cancer treatment given). Patients who remain known to be alive at the date of data cut-off (last patient, last visit) will be censored at their date last known to be alive. Patients who are lost to follow-up will be censored at the point last known to be alive; however, if  $\geq 2\%$  of patients are in this category, a sensitivity summary will be produced to illustrate the overall survival assuming the patient died at the date last known in the trial. If possible, the date of death may be recovered from publically available sources such as death registries.

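### Survival follow-up ends at LPLV, which guarantees only 24 weeks, so after a stop at the interim the secondary endpoint 12-month OS may be imprecise or, with fast accrual, not estimable

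*Protocol*

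**What the plan says.** Table 9 (Section 2) lists the further efficacy endpoints: "To include Disease Control Rate, Duration of Response; Progression-free Survival; 12-month Overall Survival". Section 8.12.2.3 gives the estimator: "The estimated survival at 12 months will be read from the Kaplan Meier OS curve". It also gives the cut-off: "Patients who remain known to be alive at the date of data cut-off (last patient, last visit) will be censored", at the date last known alive.

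Data collection ends at the same date. In the synopsis (Study Procedures and Assessments), after progression "patients will continue to have their survival status checked every 12 weeks until death or the Last Patient Last Visit (LPLV) date", whichever is earlier.

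Section 8.6 ties LPLV to the point when all evaluable patients have had the potential for at least 24 weeks of follow-up. If the trial ends at the interim, "In this situation, the last patient, last visit (LPLV) will occur at this point". If some patients are still on treatment then, "only serious safety data will be collected between LPLV and the final closure date", and "An addendum (or addenda) to the CSR will be generated to report any outstanding serious safety data". If nobody is on treatment, "the study will close at the same time as the date of LPLV". Section 8.3 likewise limits the addendum to SAEs. Section 10.3 has consent cover follow-up contact until the end of the study and sets no later date.

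**The concern.** The endpoint needs information at 12 months, and the follow-up rule secures 24 weeks. On the full 56-patient path the gap largely closes by itself, because stage 1 patients are followed through the halt and all of stage 2. On the interim-stop path nothing closes it. Survival contact ends when the last of 28 patients reaches 24 weeks, and no other section keeps it open.

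An analysis plan cannot recover survival data that the protocol has stopped collecting. A named secondary endpoint could then be absent from the report or rest on a handful of patients. That matters most after an early stop for activity, when survival data would be wanted.

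**Working it through.** **Inputs.** From Section 8.1: 28 patients at the interim, futility at 5 or fewer responses, activity at 11 or more, 17 or more of 56 at the end, p0 = 0.20, p1 = 0.35. From Section 8.6: cut at last entry + 24 weeks. From Section 1.1: median survival of 13 months from the appearance of metastatic disease, used here for illustration with exponential survival. Accrual is not stated. With the synopsis figure of up to about 20 sites and an assumed 0.1 to 0.3 patients per site per month, 28 patients take 28/(20 × 0.1) = 14 months (61 weeks) down to 28/(20 × 0.3) = 4.7 months (20 weeks).

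**Step 1: the plan's own figures.** Exact binomial calculation gives one-sided alpha 0.0483, power 0.8055, futility stop under the null 0.5005, activity stop under the alternative 0.3840, and expected size 41.6 to 44.1. The protocol states 0.048, 80.6%, 50.2%, 38.4% and 42-44, so the design reproduces.

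**Step 2: how often the interim rule is met.** P(X ≤ 5) + P(X ≥ 11), n = 28:

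| True ORR | Futility | Activity | Either |
|---|---|---|---|
| 0.20 | 0.5005 | 0.0149 | 51.5% |
| 0.26 | 0.2263 | 0.0863 | 31.3% |
| 0.28 | 0.1624 | 0.1325 | 29.5% |
| 0.30 | 0.1128 | 0.1913 | 30.4% |
| 0.35 | 0.0393 | 0.3840 | 42.3% |

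**Step 3: who can reach 12 months after an interim stop.** A patient needs 52 weeks between entry and cut. The last patient has 24, so only those who entered at least 52 − 24 = 28 weeks before the last entry qualify. A cut 8 weeks later shortens this to 52 − 32 = 20 weeks. If OS starts at a consent 4 weeks before dosing, it is 24 weeks.

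**Step 4: consequence for the Kaplan-Meier value.** True 12-month survival is 0.5^(12/13) = 0.527. With full follow-up of 28 patients the standard error is √(0.527 × 0.473/28) = 9.4 points. With the cut at +24 weeks, in simulated trials (not estimable means that the longest observed time is censored before 12 months):

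- Accrual in 20 to 26 weeks: nobody can reach 12 months, and the value is not estimable in about 98% of trials. In the remainder the longest observed time happens to be a death, so the curve drops to zero.
- Accrual in 30 weeks: with evenly spaced entry 2 of 28 can reach 12 months, and both die first with probability 0.473² = 22%, which matches the simulated 21-22%. With random entry the mean span from first to last entry is 30 × 27/29 = 27.9 weeks, and the simulated figure is about 60%. The honest range is roughly 20-60%.
- Accrual in 39 weeks: 8 of 28 can reach 12 months, so about 8 × 0.527 = 4 are at risk. The SD is about 12 points.
- Accrual in 52 weeks: 13 of 28 can reach 12 months, so about 7 are at risk. The SD is about 10.5 to 11 points.

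**Step 5: the 56-patient path.** Recruitment halts for at least 24 weeks, and LPLV comes 24 weeks after the last stage 2 entry. Every stage 1 patient therefore has at least 48 weeks plus the stage 2 accrual time. The value is estimable in every simulated trial, with an SD of about 7 to 8 points against √(0.527 × 0.473/56) = 6.7.

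**The case against.** The strongest reply is that this is mainly a matter of precision on an untested secondary endpoint. A Kaplan-Meier estimate does not need 12 months from every patient, and with accrual of a year or more most of the uncertainty comes from having 28 patients. That stands.

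Non-estimability also depends on things the protocol leaves open. It needs 28 patients within about 28 weeks, or roughly 0.22 per site per month at 20 sites (28/6.44 months/20), in a trial that requires a fresh biopsy. The cut is at least 24 weeks, so it may come later. The date of enrolment that starts OS may precede first dose. Each can move a trial across the threshold, so figures close to it should not be read to the percent. That stands too.

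The stop probability mixes unlike outcomes. At 0.20 it is nearly all futility, after which a single-arm 12-month OS has little decision value. Activity stops have probability 1.5% at 0.20, 19.1% at 0.30 and 38.4% at 0.35. These figures also describe the rule being met; the DRC recommendation weighs risk and benefit as well.

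None of this supplies the missing follow-up. A reader might go further and infer that the OS estimate would be biased, or that 12-month OS is lost whatever happens. The documents support neither. Censoring at a common calendar cut is administrative and costs precision only, and the 56-patient path yields the endpoint.

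**Conclusion.** The concern holds for the interim-stop branch. Follow-up that ends at LPLV does not secure 12-month OS there. With stage 1 accrual under about 28 weeks and a cut at +24 weeks, the endpoint would almost always be missing. At about 30 weeks it is missing in roughly 20-60% of trials. At 39 weeks it rests on about 4 patients at risk, with an SD of about 12 points against 9.4. At 52 weeks or more the loss is modest.

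These sizes rest on assumed accrual, a cut at exactly 24 weeks, OS starting at about first dose, and exponential survival with a 13-month median. That median counts from first metastatic disease and may be optimistic for pre-treated patients. The primary ORR analysis and the two-stage operating characteristics are unaffected. The point should be fixed because the remedy is cheap, but it does not threaten the trial's main conclusion.

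**What to change.** Keep the ORR cut-off and the CSR timing. In the synopsis (Study Procedures and Assessments) and Section 8.6:

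- continue the existing 12-weekly telephone survival checks after LPLV until the last patient is 52 weeks from first dose, with a final status check on survivors at that date;
- add survival status to the data collected after LPLV;
- align the Study Completion and Study Closure definitions, and the OS cut-off in Section 8.12.2.3;
- widen the CSR addendum in Sections 8.3 and 8.6 to report 12-month OS;
- check whether Section 10.3 needs new consent wording, since redefining the end of the study may already cover the extra contact.

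If the sponsor prefers not to follow survival after an interim stop, the protocol should say so and report 12-month OS only where estimable, with the number at risk.

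The cost is at most 3 extra calls for each survivor with under 52 weeks at LPLV. Under the assumptions above that is about 8 to 35 calls in total after an interim stop. There is one later survival data cut, and possibly re-consent. If everyone is off treatment, the study stays open up to 28 weeks longer.

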- c) All sample times are approximate and every effort must be made to take PK samples at specified times. Actual sampling times must be recorded in order to assess result relative to BGB324 or pembrolizumab dose. Please refer to the local Laboratory Manual for full details on PK sample collection, time-points, processing, storage and shipment.
- 13 D1 of next cycle would be "D22" of the previous cycle.
- 14 A Post Treatment Visit is to be conducted up to 30 days (+/-3 days) from last dose of study drugs. Adverse events and concomitant medications must be assessed to 30 days. Some AEs must be assessed for longer (see [Section 7.4.3](#) and [Section 7.5](#)). Other assessments may be carried out between 7-30 days from last dose. Tumor imaging and disease assessment is only required where is part of next scheduled assessment (where patient has not yet progressed) or to confirm response or progression.
- 15 Tumor imaging and disease assessment will continue every 12 weeks from the last dose of study drug where the patient has not yet progressed or to confirm response or progression. An assessment of disease status, survival status and details of any anti-cancer therapies received after last dose of study drug will also be collected. Survival status (every 12 weeks) can be collected by telephone.
- 16 Echocardiogram (or MUGA) will be conducted every 6 months whilst a patient receives BGB324. If a patient discontinues BGB324 (but continues pembrolizumab), a final echocardiogram (or MUGA) will be conducted only if one is scheduled in the following 6 weeks.
- 17 Demography – race, ethnicity, gender, age (birth month and year).
- 18 Hematology and Clinical Chemistry to be assessed at a suitable time prior to administration of study treatment(s).

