### 6.6.3 Pembrolizumab dose modifications

Adverse events (both non-serious and serious) associated with pembrolizumab exposure may represent an immunologic etiology. These AEs may occur shortly after the first dose or several months after the last dose of treatment. Pembrolizumab must be withheld for drug-related toxicities and severe or life-threatening AEs as per [Table 14](#) below. See [Section 6.11](#) for supportive care guidelines, including use of corticosteroids.

Table 14: Dose modification guidelines for pembrolizumab drug-related adverse events

Toxicity	Hold Treatment For Grade	Timing for Restarting Treatment	Treatment Discontinuation
Diarrhea/Colitis	2-3	Toxicity resolves to Grade 0-1	Toxicity does not resolve within 12 weeks of last dose or inability to reduce corticosteroid to 10 mg or less of prednisone or equivalent per day within 12 weeks
	4	Permanently discontinue	Permanently discontinue
AST, ALT, or Increased Bilirubin	2	Toxicity resolves to Grade 0-1	Toxicity does not resolve within 12 weeks of last dose
	3-4	Permanently discontinue (see exception below) a	Permanently discontinue
Type 1 diabetes mellitus (if new onset) or Hyperglycemia	T1DM or 3-4	Hold pembrolizumab for new onset Type 1 diabetes mellitus or Grade 3-4 hyperglycemia associated with evidence of beta cell failure	Resume pembrolizumab when patients are clinically and metabolically stable
Hypophysitis	2-4	Toxicity resolves to Grade 0-1. Therapy with pembrolizumab can be continued while endocrine replacement therapy is instituted	Toxicity does not resolve within 12 weeks of last dose or inability to reduce corticosteroid to 10 mg or less of prednisone or equivalent per day within 12 weeks
Hyperthyroidism	3	Toxicity resolves to Grade 0-1	Toxicity does not resolve within 12 weeks of last dose or inability to reduce corticosteroid to 10 mg or less of prednisone or equivalent per day within 12 weeks
	4	Permanently discontinue	Permanently discontinue
Hypothyroidism		Therapy with pembrolizumab can be continued while thyroid replacement therapy is instituted	Therapy with pembrolizumab can be continued while thyroid replacement therapy is instituted
Infusion Reaction	2 b	Toxicity resolves to Grade 0-1	Permanently discontinue if toxicity develops despite adequate premedication
	3-4	Permanently discontinue	Permanently discontinue

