**For the time period beginning when the consent form is signed until treatment allocation, any SAEs, or follow up to a SAE, including death due to any cause other than progression of the cancer under study, that occurs to any patient must be reported within 24 hours to the Sponsor if it causes the subject to be excluded from the trial, or is the result of a protocol-specified intervention, including but not limited to washout or discontinuation of usual therapy, diet, placebo treatment or a procedure.**

**For the time period beginning at treatment allocation through 90 days following cessation of treatment, or 30 days following cessation of treatment if the subject initiates new anticancer therapy, whichever is earlier, any SAE, or follow up to a SAE, including death due to any cause other than progression of the cancer under study, whether or not related to the Sponsor's product, must be reported within 24 hours to the Sponsor either by electronic media or paper.** Electronic reporting procedures can be found in the electronic data capture (EDC) data entry guidelines. Paper reporting procedures can be found in the Investigator Trial File Binder (or equivalent).

Additionally, any SAE, considered by an investigator who is a qualified physician to be related to the Sponsor's product that is brought to the attention of the investigator at any time following consent through the end of the specified safety follow-up period specified in the paragraph above, or at any time outside of the time period specified in the previous paragraph also must be reported immediately to the Sponsor.

All patients with SAE must be followed up for outcome.

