#### 7.4.3.2 Events of clinical interest

Selected non-serious and serious AEs are also known as Events of Clinical Interest (ECI) and must be reported to the Sponsor.

**For the time period beginning when the consent form is signed until treatment allocation, any ECI, or follow up to an ECI, that occurs to any subject must be reported within 24 hours to the Sponsor if it causes the subject to be excluded from the trial, or is the result of a protocol-specified intervention, including but not limited to washout or discontinuation of usual therapy, diet, placebo treatment or a procedure.**

**For the time period beginning at treatment allocation through 30 days following cessation of treatment, any ECI, or follow up to an ECI, whether or not related to the Sponsor's product, must be reported within 24 hours to the Sponsor, either by electronic media or paper.** Electronic reporting procedures can be found in the EDC data entry guidelines. Paper reporting procedures can be found in the Investigator Trial File Binder (or equivalent).

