### **8.3 Statistical Analysis Plan**

Detailed statistical analysis information will be provided separately in the Statistical Analysis Plan (SAP). The SAP will detail all data handling rules e.g. full definition of patient populations for analysis, including the management of missing values and the handling of data for patients lost to follow-up or missing other important information. The SAP will also outline protocol deviation criteria. Any deviations to the planned analyses specified or populations defined within the SAP will be justified in writing and presented within the final clinical study report. It will also describe the rules for handling of missing data points for the primary, secondary and exploratory endpoints.

An interim analysis will be performed after 28 evaluable patients have had the potential to have at least 24 week follow-up (enabling each patient to have the potential for at least 2 ‘on treatment’ disease assessment scans). Recruitment will be halted during this period and until the interim analysis has been conducted.

The SAP will fully describe the efficacy analyses and descriptive summaries that will be undertaken for both the interim and final analyses. All efficacy endpoints (ORR, DoR, PFS, DCR and OS) will be summarized and described for both the interim and final analyses. See [Section 8.11](#) and [Section 8.12](#) for further details.

Summaries of ORR by PD-L1 and Axl expression will be provided for both the interim and final analyses.

The clinical database lock for the final analysis will occur after the final patient has had the potential to be followed for 24 weeks and after all data are reconciled (i.e. “cleaned”) for all patients who participate in the study. A single clinical study report (CSR) will be generated. The SAP will be finalized and signed before the database lock.

An addendum (or addenda) to the CSR will be generated to report SAEs from patients remaining on treatment at the time of the LPLV patients to closure of the study (defined as every patient completing their study combination treatment) ([Section 8.6](#)).

The main data analyses intended for this trial are briefly described in this section and in [Section 8.11](#) and [Section 8.12](#). The SAP will provide full details of all planned data analyses for the primary, secondary and exploratory objectives of the study.

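### Sections 8.3 and 8.6 restrict safety collection after LPLV and close the study at about day 30, contradicting the AE, ECI, SAE and pregnancy windows in Section 7

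*Protocol*

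**What the plan says.** **Section 8.6** sets LPLV at the point when all evaluable patients have had the potential for 24 weeks of follow-up, or at the interim analysis if the trial stops there. It foresees that some patients will still be on treatment. From then on, "only serious safety data will be collected between LPLV and the final closure date". The end point is also fixed there: "Study Closure is defined by completion of the last dose of study drug and post treatment visit".

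**Tables 4 and 5, footnote 14** times that visit: "A Post Treatment Visit is to be conducted up to 30 days (+/-3 days) from last dose of study drugs". The same footnote adds: "Some AEs must be assessed for longer".

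**Section 8.3** describes the addendum to the clinical study report as covering SAEs in patients still on treatment at LPLV, up to "closure of the study (defined as every patient completing their study combination treatment", with a cross-reference to Section 8.6. It does not mention the Post Treatment Visit.

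**Section 7** sets the reporting duties by each patient's own end of treatment:
- Section 7.1: all AEs, serious or not, to 30 days.
- Section 7.4.3.1, SAEs: "For the time period beginning at treatment allocation through 90 days following cessation of treatment", cut to 30 days once new anticancer therapy starts. SAEs judged related are reportable at any time.
- Section 7.4.3.2, ECIs: "For the time period beginning at treatment allocation through 30 days following cessation of treatment, any ECI", reported within 24 hours. The definition includes non-serious events.
- Section 7.7: pregnancies and lactations to 120 days, or 30 days with new therapy. It states that these are not AEs.

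None of these subsections mentions LPLV or study closure.

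**The concern.** LPLV is an analysis milestone, not the end of dosing. Treatment may run to 106 weeks (Section 4.2), so a patient can be on both drugs long after LPLV. During that time Section 7 tells the site to report every AE and every ECI, while Section 8.6 tells it that only serious data are collected. A site cannot obey both.

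Two kinds of information are at risk. The first is non-serious events in patients still on drug, including the two listed ECIs when they are not serious: an overdose without symptoms, and the combined transaminase and bilirubin finding that the protocol uses as its Hy's Law screen. The second is the tail of the SAE and pregnancy windows in the patients who stop last. The protocol itself expects late immune events: "These AEs may occur shortly after the first dose or several months after the last dose of treatment" (Section 6.6.3). Section 4.1 adds that the two drugs had not been combined in patients before.

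**Working it through.** There is no stated figure to reproduce. The check compares the texts and counts days.

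**Inputs.** Post Treatment Visit at day 30 ± 3, so day 27 to 33 (footnote 14). Windows after the end of treatment: all AEs 30 days (7.1), ECIs 30 days (7.4.3.2), SAEs 90 days (7.1, 7.4.3.1), pregnancy and lactation 120 days (7.7). Minimum potential follow-up at LPLV is 24 weeks (8.6). Maximum treatment is 106 weeks (4.2).

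**Step 1: closure against each window.** Uncovered days = required window − day of the visit, for the patient whose last dose defines closure:

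| Duty | Window | Visit day 27 | Day 30 | Day 33 |
|---|---|---|---|---|
| All AEs, ECIs | 30 | 3 | 0 | none |
| SAEs | 90 | 63 | 60 | 57 |
| Pregnancy, lactation | 120 | 93 | 90 | 87 |

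At day 30 this is 60/90 = 67% of the SAE window and 90/120 = 75% of the pregnancy window. Closure costs AEs and ECIs almost nothing; their conflict comes from the serious-only limit.

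**Step 2: who is affected by closure.** A patient whose last dose came *d* days before the final patient's last dose has *d* + 30 days covered. The SAE window is cut if *d* + 30 < 90, that is *d* < 60. The pregnancy window is cut if *d* + 30 < 120, that is *d* < 90. A patient who has started new anticancer therapy has a 30-day window and loses essentially nothing. Because related SAEs are reportable at any time, the SAEs exposed are those not judged related, from about day 31 to day 90.

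**Step 3: length of the serious-only period.** For a patient at week 24 at LPLV who completes treatment, 106 − 24 = 82 weeks of dosing remain (81 if 35 cycles are counted as 35 × 3 = 105 weeks). Adding the 30-day visit gives 82 × 7 + 30 = 604 days. Throughout, Section 7 requires non-serious AEs and ECIs that Section 8.6 does not collect. The limit also touches patients already off drug at LPLV but within 30 days of their last dose.

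**Step 4: the addendum.** Section 8.3 restricts it to patients on treatment at LPLV. A patient who stopped shortly before LPLV has an SAE window running past it but falls outside that scope.

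**Step 5: the closure definitions.** Section 8.6 requires the last dose and the Post Treatment Visit. Section 8.3 requires only completion of combination treatment. Read literally, the second falls earlier.

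**The case against.** The best counter-argument is that the protocol runs on two tracks. Section 8.6 deals with completion, database lock and the report; Section 7 deals with reporting to the sponsor, with clocks that run from each patient's last dose. SAEs and ECIs go to the drug safety group on their own form (7.5), related SAEs are reportable indefinitely, pregnancies are followed to outcome, and nothing in 8.6 cancels scheduled visits or laboratory tests. The closure wording in 8.3 points to 8.6 and may be shorthand.

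Much of this is fair, and it narrows the point. It does not remove the word limiting collection to serious data, nor the closure at about day 30. If Section 7 is meant to prevail, 8.6 is wrong as written and needs correcting.

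Several stronger readings are tempting, but the documents do not support them:
- *The longest-treated patients lose follow-up, and no earlier data exist for such exposure.* Recruitment halts at 28 patients until they have 24 weeks of potential follow-up (8.2.2, 8.3), and final LPLV needs another 24 weeks for Stage 2. If the trial continues, Stage 1 patients are therefore at least 24 + 24 = 48 weeks from first dose at LPLV, with the full AE duty in force until then. The patient with 82 weeks still to go is the one with the shortest exposure.
- *No ECIs at all are collected after LPLV.* Serious ECIs remain serious data, and AEs associated with an overdose count as serious for collection (7.4.3.1). Only non-serious ECIs are in doubt.
- *The main report understates late toxicity.* Its data are locked at LPLV in any case. Only the addendum is affected.

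**Conclusion.** The contradiction stands in the operative text and should be corrected. Sections 8.3 and 8.6, followed as written, drop safety information that Sections 7.1, 7.4.3 and 7.7 require. The size is the serious-only period of Step 3, plus the SAE and pregnancy tails of Step 1 for the last patients to stop.

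The figures assume that a patient completes the maximum treatment after LPLV, that closure follows the Section 8.6 definition, and that no new anticancer therapy has begun. The number of patients affected cannot be derived from the protocol and could be small. Sample size, error rates and the response-rate analysis do not depend on this point.

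**What to change.** Reconcile Sections 8.3 and 8.6 with Section 7 by amendment:

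1. State that after LPLV, SAEs, ECIs (serious or not) and pregnancies and lactations continue to be collected for their full Section 7 windows.
2. Settle non-serious AEs that are not ECIs: either keep the Section 7.1 duty after LPLV, or amend 7.1 to say explicitly that it stops at LPLV. Listing only SAEs, ECIs and pregnancies in 8.6 would leave 8.6 and 7.1 in conflict.
3. Use one definition of study closure in 8.3 and 8.6, tied to the end of the last patient's applicable Section 7 windows, including the 30-day limit once new therapy starts.
4. Extend the addendum to every patient whose window runs past LPLV, including those who stopped shortly before it.

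**Cost.** The change is amendment wording, and no new procedure is needed. The safety database stays open about 60 days longer for SAEs and about 90 days longer for pregnancy reporting. A brief separate contact is needed, because the 12-weekly survival checks after progression end at LPLV (Synopsis, Study Procedures and Assessments) and cannot be relied on. Keeping the full AE duty would add data entry for patients still on drug.
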